6.7.3 Clinical Laboratory Evaluations

For the purposes of summarization in both the tables and listings, all laboratory values will be converted to standardized units. If a lab value is reported using a non-numeric qualifier (eg, less than (<) a certain value, or greater than (>) a certain value), the given numeric value will be used in the summary statistics, ignoring the non-numeric qualifier.

If a patient has repeated laboratory values for a given time point, the value from the last evaluation will be used. Laboratory test results will be summarized according to the scheduled sample collection time point. Change from baseline will be presented. Scheduled laboratory along with unscheduled lab test results will be listed. Unscheduled laboratory test results will be included in the laboratory shift tables.

Lab parameters to be analyzed are as follows:

- Hematology: Hematocrit, Hemoglobin, Platelet count, Leukocytes with differential, Neutrophils (ANC).

- Chemistry: albumin, alkaline phosphatase (ALP), alanine aminotransferase (ALT), aspartate aminotransferase (AST), bilirubin (total), blood urea nitrogen, calcium, bicarbonate (HCO_3) or carbon dioxide (CO_2), creatinine, standard C-reactive protein, chloride, glucose, lactate dehydrogenase, magnesium, phosphate, potassium, sodium, urate, thyroid function test.

Whenever available, laboratory values will be assigned toxicity grades using the NCI CTCAE Version 5.0. Shift tables will be constructed for laboratory parameters either using CTCAE grade or based on low/medium/high compared to normal ranges on patients who have both baseline and at least one post-baseline assessment. Individual platelet and ANC profiles will be generated for each dose level. Mean values over time for platelets and ANC will be produced.

6.7.4 Vital Signs

For dose escalation cohorts, descriptive statistics for vital sign results (diastolic and systolic blood pressure, respiratory rate, pulse rate, oxygen saturation and body weight) will be summarized by dose levels as follows:

- Baseline value (C1D1 or screening if C1D1 is not available).
- Minimum post-baseline value.
- Change to Minimum post-baseline value.
- Maximum post-baseline value.
- Change to Maximum post-baseline value.

Changes to the minimum and maximum post-baseline values will be calculated relative to the baseline value.

6.7.5 12-Lead ECGs

ECG data (ventricular rate, RR interval, PR interval, QT interval, and QTcF interval) will be summarized by dose levels as follows:

- Baseline value (C1D1 or screening if C1D1 is not available).
- Minimum post-baseline value.
- Change to Minimum post-baseline value.
- Maximum post-baseline value.
- Change to Maximum post-baseline value.

Changes to the minimum and maximum post-baseline values will be calculated relative to the baseline value.

In addition, a categorical analysis of QTcF intervals will be performed for each time point. The number and percentage of patients in each QTcF interval (<450 msec, 450-480 msec, >480-

<500 msec, and ≥ 500 msec) will be summarized at baseline and each of the subsequent time points. Categories of changes from baseline (≥ 30 msec and ≥ 60 msec) will be summarized as well.

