##### 8.1.1.2 Administration

Modakafusp alfa will be administered by infusion over 1 hour ( $\pm$ 10 minutes). Any decrease in infusion duration must be discussed with and agreed on by the sponsor.

Daratumumab SC will be administered before modakafusp alfa on days on which both agents are given on the same visit day. At least 30 minutes should elapse between the completion of the injection of daratumumab SC and the initiation of the infusion of modakafusp alfa.

If a patient presents with an IRR at any dose level, the duration of the infusion may be extended per the investigator's discretion. Infusion and pharmacy staff are advised to be prepared accordingly for either a planned, extended infusion time or for potential infusion interruptions. See the pharmacy manual for additional guidance.

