### 9.5.11 ECG

A 12-lead ECG will be obtained at the time points specified in [Appendix A](#). A qualified person will interpret the ECG locally. Additional ECGs may be obtained as clinically indicated at the discretion of the investigator.

Any ECG finding that is judged by the investigator as clinically significant (except at the screening visit) will be considered a TEAE, recorded on the source documentation and in the eCRF, and monitored as described in Section [10.3](#).

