## **Footnotes for Appendix A Tables 1 and 2**

- a Written informed consent must be obtained before performing any protocol-specific procedure. Test results from routine clinical management are acceptable for screening if obtained within the specified time window.
- b Height will be measured only at the screening visit.
- c All patients will have 1 standard local ECG collected and read locally at screening and at the end of dosing (+30 minutes) of all planned medications in the clinic on the days indicated.
- d Vital signs will be measured at predose of each drug administration (eg, predose of daratumumab SC and predose of modakafusp alfa for modakafusp alfa in combination with daratumumab SC treatment), and after completing the administration of the last treatment medication (eg, after the completion of modakafusp alfa administration when daratumumab SC and modakafusp alfa are administered sequentially) on the days indicated. Vital signs include temperature, pulse, respiratory rate, oxygen saturation, and blood pressure. Vital signs will be measured at any time a patient complains of symptoms consistent with IRR or clinically indicated.
- e Clinical imaging assessments to summarize status of known lesions should be based on available imaging at each respective time point.
- f In case of an IRR, collect serum sample for circulating biomarkers, blood sample for flow cytometry, blood sample for RNA, and serum sample for immunogenicity (ADA), if clinical management of patient allows. Any decrease in infusion duration of modakafusp alfa must be discussed with and agreed on by the sponsor. If a patient presents with an IRR at any dose level, the duration of the infusion for modakafusp alfa may be extended per investigator's discretion. Total time from modakafusp alfa dosing solution preparation until end of infusion must not exceed 7 hours. Infusion and pharmacy staff are advised to be prepared accordingly for either a planned, extended infusion time or for potential infusion interruptions. See modakafusp alfa Pharmacy Manual for additional guidance.

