6.0 STATISTICAL ANALYSIS

6.1 General Considerations

All statistical analyses will be conducted using SAS® Version 9.4 or later.

For categorical variables, the count and proportions of each possible category value will be tabulated. The denominator for the proportion will be based on the number of subjects in the

CONFIDENTIAL

populations. For continuous variables, the mean, median, standard deviation, minimum, and maximum values will be presented for all patients in the relevant population.

All 95% confidence intervals will be reported as 2-sided. No formal statistical comparisons will be performed between dose levels.

Baseline values are defined as the last observed value before the first dose of any study drug.

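### The SAP's ECG baseline is the Cycle 1 Day 1 recording, which the protocol schedules only after both drugs have been given

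*SAP*

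**What the plan says.** SAP 6.7.5 summarizes ventricular rate and the RR, PR, QT and QTcF intervals at baseline, at the post-baseline minimum and maximum, and as change to each. The baseline line reads "Baseline value (C1D1 or screening if C1D1 is not available". The section also tabulates absolute QTcF bands at each time point and adds: "Categories of changes from baseline (≥ 30 msec and ≥ 60 msec) will be summarized as well".

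SAP 6.1 gives a general rule: "Baseline values are defined as the last observed value before the first dose of any study drug".

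The ECG rows of protocol Appendix A Tables 1 and 3 mark screening, C1D1 and Cycle 2 Day 1 in the first two cycles. Footnote c, worded the same for both phases, specifies "1 standard local ECG collected and read locally at screening and at the end of dosing (+30 minutes) of all planned medications". Both drugs are given on C1D1, and protocol 8.1.1.2 fixes the order: "Daratumumab SC will be administered before modakafusp alfa on days on which both agents are given on the same visit day". Protocol 9.5.11 adds: "Additional ECGs may be obtained as clinically indicated at the discretion of the investigator".

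**The concern.** A baseline should be free of study-drug effect. The C1D1 ECG is not, because it is taken once both agents are in. If the first infusion changes QTcF or heart rate, that change becomes part of the reference. It then disappears from the first-exposure result and is subtracted from every later one.

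ECG change from baseline is a named component of the safety evaluation (protocol 13.1.8, SAP 6.7), and safety and tolerability are the primary objective of phase 1. The change categories in 6.7.5 are where a QTcF signal would show in the tables, and they depend entirely on this reference value.

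**Working it through.** The plan states no figure for this point, so the check is of timing, followed by algebra and an illustration.

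**1. Which ECGs are planned before the first dose**

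| Recording | Timing relative to first dose | Meets SAP 6.1? | Role under SAP 6.7.5 |
|---|---|---|---|
| Screening | Before | Yes | Fallback only |
| C1D1 | After both drugs | No | Preferred baseline |
| Unscheduled, before dosing on C1D1 | Before, but only if clinically indicated | Yes | Not addressed |

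The only planned ECG that satisfies 6.1 is screening. 6.7.5 uses it only when the C1D1 ECG is missing.

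**2. What the protocol treats the C1D1 ECG as**

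Protocol 9.5.11 makes a clinically significant ECG finding a TEAE at every visit except screening. The protocol therefore treats the C1D1 ECG as on-treatment, while the SAP treats it as baseline.

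**3. Vital signs differ**

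SAP 6.7.4 uses the same baseline line, but footnote d provides that "Vital signs will be measured at predose of each drug administration". A pre-dose C1D1 value exists there, and the wording only needs to say which C1D1 reading is meant. For ECG no such reading is scheduled.

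**4. Algebra of the bias**

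Let *S* be the screening value, *B* the end-of-dosing C1D1 value, *d* = *B* − *S*, and *Y* any later value.

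- Change under 6.7.5 = *Y* − *B* = (*Y* − *S*) − *d*.
- The bias relative to a pre-dose baseline is −*d*. With *d* > 0, rises shrink and falls grow; with *d* < 0, the reverse.
- At C1D1 the change is *B* − *B* = 0 by construction.

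Example with assumed values, for a later QTcF 35 msec above screening: *d* = 0 gives 35 (counted as ≥30); *d* = 10 gives 25 (not counted); *d* = 25 gives 10 (not counted).

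**5. Illustration for the ≥30 msec category**

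Assumptions, none of them from the documents: the change is Normal; its SD is 15 or 20 msec under either baseline; and the acute effect *e* present at the end of C1D1 dosing recurs at the later end-of-dosing ECG. With a pre-dose baseline, P(change ≥ 30) = 1 − Φ((30 − *e*)/SD). With the C1D1 baseline the effect cancels, giving 1 − Φ(30/SD).

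| *e* (msec) | Pre-dose baseline, SD 15 | Pre-dose baseline, SD 20 | C1D1 baseline, SD 15 | C1D1 baseline, SD 20 |
|---|---|---|---|---|
| 5 | 0.048 | 0.106 | 0.023 | 0.067 |
| 10 | 0.091 | 0.159 | 0.023 | 0.067 |
| 15 | 0.159 | 0.227 | 0.023 | 0.067 |

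In patients at one time point, the smallest gap is 0.048 − 0.023 = 0.025 and the largest is 0.227 − 0.067 = 0.160. For 6 patients at a phase 1 dose level this is 0.15 to 0.96 of a patient. For a planned phase 2a arm of 20 it is 0.5 to 3.2 patients.

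**6. What drops out of the tables**

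The C1D1 ECG is the only scheduled on-treatment ECG in Cycle 1; the next is Cycle 2 Day 1. Used as baseline, it leaves the post-baseline minimum, maximum and change categories. A patient who stops during Cycle 1 then has only the end-of-treatment ECG as a scheduled post-baseline value. The absolute bands are also mislabelled. Exclusion criterion 13 bars QTcF above 480 msec at entry, so a patient who first reaches 500 msec or more after the first infusion would be shown in the top band at baseline.

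**The case against.** The strongest reply is that SAP 6.1 already requires a pre-dose baseline, so 6.7.5 should be read under it: take C1D1 if a pre-dose ECG exists, otherwise screening. The line shared with 6.7.4 suggests wording carried over from vital signs rather than a deliberate choice. That may be how it arose. However, 6.7.5 is the more specific rule, names C1D1 first, and would ordinarily be the one programmed. If 6.1 is meant to govern, 6.7.5 still needs correcting.

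The consequences also have limits:

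- No primary or secondary endpoint uses ECG change. Escalation runs on DLTs, and dose levels are not formally compared.
- A clinically significant C1D1 ECG finding would still be captured as a TEAE, and a long C1D1 QTcF would still be counted in the absolute bands, although labelled baseline.
- Protocol 4.5.1.1 reports no direct drug-induced cardiovascular changes in the monkey studies. Against that, protocol 4.5.1.2 lists tachycardia among the infusion reactions, which occurred in 18.9% of patients in the single-agent study, so an acute heart-rate effect is plausible.

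These points restrict the damage to the descriptive change summaries; they do not make the post-dose baseline correct.

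Finally, screening can be up to 21 days before dosing and precedes the corticosteroid and antihistamine premedication, so change from screening mixes premedication with study-drug effect. That is a real limit on interpretation, but it does not justify a reference value taken after study drug.

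**Conclusion.** The concern holds. As written, SAP 6.7.5 takes a post-dose ECG as baseline whenever the protocol schedule is followed, and it conflicts with SAP 6.1. This follows from the timing alone and needs no assumption about drug effect.

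The bias in each change is minus the shift present at the end of C1D1 dosing. Its size and sign are unknown because the documents give no QTcF effect. Under the stated assumptions, effects of 5, 10 and 15 msec would give 5-11%, 9-16% and 16-23% of patients at or above 30 msec from a pre-dose baseline; the C1D1 baseline would report 2-7% in every case. These percentages are illustrative only. The loss of the first on-treatment ECG from the post-baseline tables is certain. It should be corrected before the ECG tables are programmed.

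**What to change.** In SAP 6.7.5, replace the baseline line with text to this effect: *ECG baseline is the most recent ECG recorded before any study drug is given; under the current schedule this is the screening ECG. The C1D1 end-of-dosing ECG is the first post-baseline time point and enters the minimum, maximum and categorical summaries.* Worded this way, a valid unscheduled pre-dose ECG on C1D1 would still be used, and 6.7.5 agrees with 6.1.

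In SAP 6.7.4, state that the C1D1 baseline for vital signs is the reading taken before daratumumab, since readings are taken both before and after dosing that day.

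A table footnote should say that the ECG reference precedes premedication and may be up to 21 days before first dose.

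The cost is one SAP line for ECG, a clarifying phrase for vital signs and a footnote. No new data, visits or protocol change are needed.

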6.7.6 Other Observations Related to Safety

Shifts from baseline to the worst post-baseline ECOG score will be tabulated.

6.8 Pharmacokinetic, [REDACTED], and Biomarker Analyses

6.8.1 Pharmacokinetic Analysis

6.8.1.1 Serum Modakafusp alfa Concentrations

Blood samples will be collected at prespecified time points as described in the study protocol for the measurement of serum modakafusp alfa and daratumumab concentrations. Individual serum concentration data will be listed by patient, dose level, study day, and sampling time. Both nominal (scheduled) and actual sampling times will be presented in the listings.

Serum modakafusp alfa and daratumumab concentrations will be summarized by nominal time post dose, grouped by dose level, nominal infusion duration, and study day by phases (escalation and dose finding). Summary statistics will be reported at nominal sampling times; means will be reported if the number of observations above the lower limit of quantitation (NALQ) is $\geq 50\%$ of the number of patients. The summary statistics will consist of: N, NALQ, arithmetic mean, standard deviation (SD), coefficient of variation (CV), geometric mean, geometric CV, median, min, and max. The SD and CV will be reported on at least 3 non-missing values. Modakafusp alfa concentrations that are below the limit of quantitation (BLQ) will be set to zero for calculation of summary statistics, except for geometric means, where BLQ values will be considered missing.

Concentration data that are considered anomalous may be excluded from the concentration summaries and plots. Evidence or explanations will be provided in the clinical study report to justify the exclusion of concentration data.

Mean and individual modakafusp alfa and daratumumab serum concentration data will be plotted over nominal sampling time, grouped by dose level, nominal infusion duration, and study day on both linear and semi-logarithmic scales. Mean and individual serum concentrations will be plotted over time (labeled with cycle number), grouped by dose level on a linear scale by phases (escalation and dose finding). Visual inspection of the serum concentration-time plots will be used to make inferences regarding the attainment of PK steady-state by cycle. BLQ values will be plotted as zero on a linear scale and treated as missing on a semi-logarithmic scale.

6.8.1.2 Serum PK Parameters (Phase I Dose Escalation)

The serum PK concentration-time course data will be used to calculate standard PK parameters using noncompartmental methods with Phoenix WinNonlin.

Actual sampling times will be used for the calculation of PK parameters. In the event that actual collection times are either unreliable or missing, nominal collection times will be used. For the calculation of PK parameters, serum concentrations of modakafusp alfa that are BLQ will be treated as zero prior to t_{max} , missing between t_{max} and the time of the last measurable concentration, and the concentration-time curve will be considered to have terminated at the time of the last measurable concentration. If measurable concentrations are near the lower limit of quantification (LLOQ) or imbedded between BLQ concentrations, these values may be excluded at the discretion of the Clinical Pharmacologist. Concentration data that are considered anomalous may not be used in the calculation of PK parameters; evidence or explanations will be provided in the clinical study report to justify the exclusion of data. In addition, patients with several missing samples around the expected T_{max} and patients for whom AUC estimation was considered not be reliable due to several missing samples (50% or more of the data are missing) may be excluded from the PK parameter (Cmax and/or AUC) calculation and PK parameter summary.

The following PK parameters for modakafusp alfa will be determined, as permitted by data:

- C_{max} .
- t_{max} .
- AUC_{∞} .
- AUC_{last} .
- λ_z .
- $t_{1/2z}$.
- CL .
- V_{ss} .
- Accumulation ratio based on AUC_{last} .

[figure not shown]
[figure not shown]
[figure not shown]
[figure not shown]
[figure not shown]
[figure not shown]
The following PK parameters for daratumumab will be determined, as permitted by data:

- C_{max} .
- t_{max} .
- C_{trough} (for daratumumab)
- AUC_{∞} .
- AUC_{last} .

Individual PK parameters will be presented in listings, PK parameters for Cycle 1 Day 1, Cycle 1 Day 15, Cycle 2 Day 1, and Cycle 2 Day 15, as appropriate, will be summarized and grouped by dose level, and study day by phases (escalation and dose finding). The SD and CV will be reported on at least 3 non-missing values. Except for t_{max} , the summary statistics will consist of: N, mean, SD, CV, geometric mean, geometric CV, median, min, and max. The summary statistics for t_{max} will consist of: N, median, min, and max.

The PK data collected in this study (phase 1 dose escalation and phase 2 dose finding) are intended to contribute to future population PK analyses of modakafusp alfa. These population PK analyses may include data collected in other modakafusp alfa clinical studies. The analysis plan for the population PK analysis will be separately defined, and the results of these analyses will not be reported in the clinical study report.

6.8.2

6.8.3 Immunogenicity Analysis

The immunogenicity of modakafusp alfa will be assessed by determining anti-modakafusp alfa antibody (ADA) incidence and characteristics (eg, titer and specificity) and by determining neutralizing antibody (NAb) incidence. All ADA and NAb data will be listed. Percent of patients with positive ADA or NAb, percent of patients with positive ADA by domain specificity, and summary statistics of ADA titer at each timepoint will be summarized by dose levels by study phases (escalation and dose finding). Percent of patients with positive ADA and NAb at baseline and positive ADA (final result and by domain specificity) and NAb at any post-baseline time point during the study will be summarized. Additional summary of the ADA kinetics including transient- vs. persistent-ADA, preexisting ADA, treatment-induced, or treatment-boosted ADA will be summarized, as applicable. ADA titer distribution over time will be presented through a boxplot on a logarithmic scale. 

